Cinnamon Trial-lifestyle iNtervention Plus Water-soluble Cinnamon
Extract On loweriNg Blood Glucose in Pre-diabetics

NCT01301521

January 24, 2018

**PROTOCOL FOR CLINICAL INVESTIGATION – NON-EXEMPT HUMAN
(Wilford Hall Ambulatory Surgical Center – WHASC)
PROTOCOL SUMMARY**

1. Title:

Cinnamon Trial —assessment of the effect of lifestyle intervention plus water-soluble cinnamon extract on lowering blood glucose in pre-diabetics: A randomized, double-blind, multicenter, placebo controlled TRIAL .
FWH20110035H

2.0. Principal Investigator (PI):

Nellis AFB PI:

Name	[name]
Rank/Corps or Civilian Rating	Col
Date of IRB Approved CITI Training	12/28/17
Branch of Service	USAF
AD Mil/DoD Civilian/Ctr/Non-DoD Civ	AD Mil
Department & Base	Graduate Medical Education, Nellis AFB
Phone & [contact]
E-Mail Address & AKO/DKO E-Mail Address	[contact]

3.0. Research Plan:

3.1. Purpose:

The purpose of this study is to assess whether water-soluble cinnamon extract plus aggressive lifestyle intervention is effective in lowering blood glucose in pre-diabetic patients when compared to aggressive lifestyle therapy plus placebo.

3.2. Hypotheses, Research Questions or Objectives:

Does water-soluble cinnamon extract have an effect on fasting glucose, hemoglobin A1c, lipid panel, and waist circumference in pre-diabetic patients who are already undergoing aggressive lifestyle therapy?

This study has the following goals:

1. Determine the length of time to diagnosis of diabetes using any of the ADA criteria.
2. Determine:
 - a) Fasting glucose,
 - b) Hemoglobin A1c,
 - c) LDL, cholesterol, and
 - d) Waist circumference (in inches).

4. Brief Summary of the study:

We are studying whether water-soluble cinnamon extract (Cinnulin PF) plus standard of care aggressive lifestyle therapy is effective in lowering blood glucose when compared to placebo plus standard of care aggressive life style therapy. Eligible subjects will be recruited from any form and any stage of “standard” lifestyle intervention for pre-diabetes at an individual base. “Standard” lifestyle intervention for pre-diabetes could include Group Lifestyle Balance (GLB), nutrition classes, Better Body/Better Life, or anything an investigator certifies as standard practice at that base. Subjects will take either 1 gram (2-500 milligram (mg) capsules) of water-soluble cinnamon extract (Cinnulin PF) or 2 placebo pills (gelatin capsule filled with wheat bran) once a day for 1 year plus 1 additional year of follow-up. This is a randomized, double-blind, multicenter, placebo-controlled study which will enroll subjects at the Mike O’Callaghan Military Medical Center at Nellis AFB (Nellis AFB). All subjects will be Nellis AFB DoD beneficiaries. Informed Consent and HIPAA Authorization will be obtained. After randomization, subjects will receive either 1 gram (2-500 mg capsules) of water-soluble cinnamon extract or placebo from the pharmacy--thus investigators and subjects will be blinded as to if they are taking Cinnulin PF or 2 placebo pills. Subjects will be permitted to have usual medical care for other co-morbid, preventive, and acute conditions. Analysis will be performed using intention-to-treat principles for missing data (the carry-forward method to impute missing data will be used). Subjects will bring in any remaining water-soluble cinnamon extract or placebo to determine adherence rates to the study protocol.

5. Subjects:

Subjects will be recruited from any form and any stage of “standard” lifestyle intervention for pre-diabetes at an individual base. “Standard” lifestyle intervention for pre-diabetes could include Group Lifestyle Balance (GLB), nutrition classes, Better Body/Better Life, or anything an investigator certifies as standard practice at that base. No special populations (i.e. children, prisoners, pregnant women, mentally disabled persons, or economically or educationally disadvantaged persons) will be eligible for this study.

6. Inclusion/exclusion criteria:

Inclusion:

- Patients will be Nellis AFBDOD beneficiaries, ages 18-65 years.
- Diagnosis of pre-diabetes (defined as a fasting plasma glucose (FPG) 100-125mg/dl, Hemoglobin A1c 5.7-6.4%, or a 2-hour oral glucose tolerance test (OGTT) 140-199).

Exclusion:

- Patients who are less than 18 yrs of age or greater than 65 years of age.
- Patients who are known to have or develop during the study any of the following upon review of their medical record:
 - o Diabetes Mellitus (defined as fasting plasma glucose (FPG) \geq 126mg/dl, hemoglobin A1C \geq 6.5%, or a 2-hour oral glucose tolerance test (OGTT) \geq 200mg/dl)
 - o Stage 3 kidney disease or worse
 - o Renal insufficiency defined as a glomerular filtration rate (gfr) of less than 60ml
 - o Celiac disease
 - o Insulinoma
 - o Cushing's disease
 - o Hyperthyroidism
 - o Acromegaly
 - o Pheochromocytoma
 - o Addison's disease
 - o Galactosemia
 - o Glycogen storage disease
 - o Hereditary fructose intolerance
- Patients taking any of the following:
 - o Cinnamon as a dietary supplement
 - o Daily oral steroids
 - o Warfarin
 - o Hypoglycemic medication
 - o Weight loss medication
 - o Digoxin, lithium, phenytoin, & theophylline (due to their narrow therapeutic indices)
- Patients who are pregnant or breast feeding
- Patients with a known allergy to cinnamon
- Patients with a known allergy to wheat

7. Number of Subjects: TOTAL NUMBER OF SUBJECTS (nation-wide/study-wide): 557

8. Use of an Investigational New Drug:

- a. Generic Name and IND Number: Cinnulin PF (cinnamomum burmanii), IND# 114078
- b. Sponsor holder of the IND Number: [name], LtCol, USAF, MC
- c. Justification for use: N/A

9. Use of an Investigational Device: N/A

10. Use of a Placebo: 2 placebo pills (gelatin capsule filled with wheat bran)

**PROTOCOL FOR CLINICAL INVESTIGATION – NON-EXEMPT HUMAN
(Wilford Hall Ambulatory Surgical Center – WHASC)**

1. Title:

Cinnamon Trial—assessment of the effect of lifestyle intervention plus water-soluble cinnamon extract on lowering blood glucose in pre-diabetics: A randomized, double-blind, multicenter, placebo-controlled **TRIAL**.

FWH20110035H

2.0. Principal Investigator (PI):

Nellis AFB PI:

Name	[name]
Rank/Corps or Civilian Rating	Col
Date of IRB Approved CITI Training & Date of AKO/DKO IRBNet Training	12/28/2017
Branch of Service	USAF
AD Mil/DoD Civilian/Ctr/Non-DoD Civ	AD Mil
Department & Base	Graduate Medical Education/Nellis AFB
Phone & [contact]
E-Mail Address & AKO/DKO E-Mail Address	[contact]

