2.1. Associate Investigators (AI): See attached A2 Study Personnel Form

2.2. Research Assistants (RA) & Coordinators (RC): See attached A2 Study Personnel Form

2.3. The research relevance of this protocol focuses on:

Diagnosis Treatment Medical Utilization/Managed Care Prevention Medical Readiness Other

2.4. Location(s):

a. Collaborating Facilities: None.

b. Air Force Sites seeking Regional IRB:

Air Force Sites	Name	Email	Phone
Nellis Air Force Base	[name], MBA/HCM, CCRP, CCRC	[contact]	[contact]

c. List study sponsors: Integrity Nutraceuticals, Inc. and AFMSA/SG9S

3. Research Plan:

3.1. Purpose:

The purpose of this study is to assess whether water-soluble cinnamon extract plus aggressive lifestyle intervention is effective in lowering blood glucose in pre-diabetic patients when compared to aggressive lifestyle therapy plus placebo.

3.2. Hypotheses, Research Questions or Objectives:

Does water-soluble cinnamon extract have an effect on fasting glucose, Hemoglobin A1c, lipid panel, and waist circumference in pre-diabetic patients who are already undergoing aggressive lifestyle therapy?

This study has the following goals:

1. Determine the length of time to diagnosis of diabetes using any of the ADA criteria.
2. Determine:
 - a) Fasting glucose
 - b) Hemoglobin A1C
 - c) LDL cholesterol, and
 - d) Waist circumference (in inches)

3.3. Significance:

Lowering hemoglobin A1c is correlated with reduced complications in Type 2 diabetes (e.g., retinopathy, nephropathy, neuropathy, vascular disease, and death). Water-soluble cinnamon extract is inexpensive, readily available, generally recognized as safe, and a non-pharmacological approach to management. According to the 2010 American Diabetes Association Guidelines, lifestyle intervention is the most effective way for diabetes. Historically, it has been difficult for subjects to adhere to lifestyle education programs and sustain meaningful weight loss without using significant resources, as in the Diabetes Prevention Study (NEJM, 2002).

3.4. Military Relevance:

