**Subjects who have had a fasting comprehensive metabolic panel test within the two weeks prior to Visit 3 will not need to have this test repeated.*
 - o Hemoglobin A1c via 1 venipuncture (5-10 mls, approximately 1-2 teaspoons of blood will be drawn).
**Subjects who have had a Hemoglobin A1c test within the two weeks prior to Visit 3 will not need to have this test repeated.*
 - o Lipid panel via 1 venipuncture (5-10 mls, approximately 1-2 teaspoons of blood will be drawn).
**Subjects who have had a lipid panel within the two weeks prior to Visit 3 will not need to have this test repeated.*

Visit 4-Month 9 (90 days after Visit 3):

- Record weight (in pounds), waist circumference) (in inches), blood pressure, verify current email address , and whether subject is taking any statins, fibrates, niacin or bile acid binding agent and, if yes, the name of drug, strength and dose.
- Study staff will also record whether subjects had any side effects to report to include cardiovascular procedures and events and other morbidity data (research-driven).
- Subjects will bring in any remaining medication to determine adherence rates to the study protocol.
- Research staff will collect the subject's Study Medication Diary and issue them a new one.
- Subjects will be told to fast for at least 10 hours prior to Visit 5.
- Refill water-soluble cinnamon extract or placebo (research-driven).
- Subjects will have standard of care blood test drawn to include:
 - o Fasting comprehensive metabolic panel (liver function tests, renal function, and plasma glucose test) via 1 venipuncture (5-10 mls, approximately 1-2 teaspoons of blood will be drawn).
**Subjects who have had a fasting comprehensive metabolic panel test within the two weeks prior to Visit 4 will not need to have this test repeated.*

- o Hemoglobin A1c via 1 venipuncture (5-10 mls, approximately 1-2 teaspoons of blood will be drawn)
**Subjects who have had a Hemoglobin A1c test within the two weeks prior to Visit 4 will not need to have this test repeated.*
- o Lipid panel via 1 venipuncture (5-10 mls, approximately 1-2 teaspoons of blood will be drawn)
**Subjects who have had a lipid panel within the two weeks prior to Visit 4 will not need to have this test repeated.*

Visit 5-Month 12 (90 days after Visit 4) *SUBJECTS STOP TAKING STUDY MEDICATIONS AT THIS VISIT:

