**Subjects who have had a fasting glucose test within the two weeks prior to Visit 8 will not need to have this test repeated.*
 - o Hemoglobin A1c via 1 venipuncture (5-10 mls, approximately 1-2 teaspoons of blood will be drawn).
**Subjects who have had a hemoglobin A1c test within the two weeks prior to Visit 8 will not need to have this test repeated.*
 - o Lipid panel via 1 venipuncture (5-10 mls, approximately 1-2 teaspoons of blood will be drawn).
**Subjects who have had a lipid panel within the two weeks prior to Visit 8 will not need to have this test repeated.*

Visit 9-Month 24 (90 days after Visit 8):

- Record: Weight (in pounds), waist circumference (in inches), blood pressure, verify current email address , and whether subject is taking any statins, fibrates, niacin or bile acid binding agent and, if yes, the name of drug, strength and dose.
- Subjects will complete the RAND 36 Item Health Survey.
- Study staff will also record whether subjects had any side effects to report to include cardiovascular procedures and events and other morbidity data (research-driven).
- Subjects will have research-driven blood tests drawn which include:
 - o Fasting plasma glucose via 1 venipuncture (5-10 mls, approximately 1-2 teaspoons of blood will be drawn).
**Subjects who have had a fasting glucose test within the two weeks prior to Visit 9 will not need to have this test repeated.*
 - o Hemoglobin A1c via 1 venipuncture (5-10 mls, approximately 1-2 teaspoons of blood will be drawn).
**Subjects who have had a Hemoglobin A1c test within the two weeks prior to Visit 9 will not need to have this test repeated.*
 - o Lipid panel via 1 venipuncture (5-10 mls, approximately 1-2 teaspoons of blood will be drawn).
**Subjects who have had a lipid panel within the two weeks prior to Visit 9 will not need to have this test repeated.*

VISIT WINDOWS: Visits have a window of plus or minus 10 days. Subjects are encouraged to come in as close to the 90 day mark as possible since they are only given a 90 day supply of IP. Postponement of any follow up visits (after subject stopped taking study medication) is authorized for up to 6 weeks in case of a temporary condition that would affect glucose tolerance (i.e. moderate to severe illness to be determined by study PI or Site AI). A note to file documenting such shall be placed in the subject's study folder and documented in the data collection form.

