ADHERENCE TO STUDY ASSIGNMENTS: Adherence to study medication will be assessed via review of the "Study Medication Diary". Compliance will be recorded both in paper format and in the electronic data collection tool. If a subject misplaces their Study Medication Diary, they will be asked to reproduce it from memory to the best of their ability. Subjects will be instructed to bring back all of the bottles regardless of whether there are empty or contain missed doses.

If at any time a subject stops taking their water-soluble cinnamon extract or placebo, they will remain in the study, will be instructed to return any pill bottles, and will continue follow-up in the study. Regardless of the amount of missed doses, all subjects will remain in the study and continue with all the study related visits. Research staff will document the missed doses and subjects will continue in the research study. If the subject decides to re-start their water-soluble cinnamon extract or placebo, they will resume the study at their last documented visit (i.e. subject stops taking water-soluble cinnamon extract or placebo at Visit 4 and decides 1 year later that they wish to resume the study, their next visit would be Visit 5).

If a subject misplaces or loses their study medication, they will be instructed to return to the pharmacy and will be given a new bottle of their assigned study medication. Since the pharmacy is not blinded, they will be able to give the medication that the subject was assigned.

If a subject forgets to bring their study medication in for their visit, they will be instructed to bring it in at their earliest convenience.

DIRECTIONS FOR TAKING MEASUREMENTS: A measuring tape to measure subjects' waist circumference will be provided to the study team. A designated study staff member will obtain the waist circumference measurements to ensure consistent measurements throughout the study.

Directions for taking waist circumference measurement: Have subject take a deep breath, blow out, and hold with abdominals tightened. Tell subjects not to suck in their stomach. Take the measurement around the largest part of their waist. Waist circumference should be recorded to the nearest ½ inch (for example 40.5").

Directions for weighing subjects: Have subject remove his/her shoes and empty pockets of any items prior to stepping on the scale. Weight should be recorded to the nearest ½ pound (for example 150.5#).

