Directions for taking height: Have subjects remove their shoes before taking their height. Height should be recorded to the nearest 1/2 inch (for example 60.5").

Directions for taking blood pressure: Have subjects sit for 5 minutes before taking blood pressure.

WITHDRAWAL PROCEDURES: If at any time during the study, the subject decides to withdraw consent they will be referred back to their Primary Care Manager (PCM). If a subject is found to be diabetic during the course of the study, they will be withdrawn and referred to their PCM to initiate standard of care treatment. Standard of care typically follows the DoD Clinical Practice guidelines for self-monitoring of blood glucose. As part of this, the Air Force provides glucometers and supplies at no charge.

ADVERSE EVENTS (AEs) AND DEVIATIONS: The Associate Investigator (AI) at each site is responsible for reviewing, categorizing, and properly reporting to the main PI AEs that occur with their subjects. The "Algorithm for Determining Whether an Adverse Event is an Unanticipated Problem" is attached to assist in guiding the research staff on the categorizing of Adverse Events, Protocol Deviations, and Serious Adverse Events.

Serious Adverse Events (SAEs) and Serious Protocol Deviations are defined as unexpected events that increase the risk to subjects and that were possibly, probably, or definitely related to the research. These must be reported to the WHASC IRB within 5 days. Each site is responsible for reporting these to [name], the local Site Principal Investigator, and [name] immediately via the "Possible Internal (Local) Reportable Unanticipated Problem Involving Risk to Subjects or Others (UPIRSO)" form.

If a subject experiences an allergic reaction during the study, they will be instructed to stop taking the study medication and seek urgent medical treatment.

Adverse Events (AEs) and Protocol Deviations that do not increase the risks to subjects like those listed in the "risks" section of this protocol are to be reported to [name], the local Site Associate Investigator and [name] as they occur or no later than the 1st workday of every month via the "WHASC Tracking Log for Adverse Events (AEs)/Protocol Deviations Not Requiring Immediate Reporting. This is done to ensure ongoing monitoring and identification of trends that may arise.

Guidance for completing the SAE/AE forms:

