PREGNANCY: Subjects must agree to take precautions to prevent pregnancy during the course of this study due to the possible effect water soluble cinnamon extract may cause an unborn child. The only completely reliable methods of birth control are total abstinence or surgical removal of the uterus. Other methods, such as the use of condoms, a diaphragm or cervical cap, birth control pills, IUD, or sperm killing products are not totally effective in preventing pregnancy. In addition, women who are breastfeeding may not participate in this study.

If a subject unintentionally becomes pregnant, they will be instructed to cease water-soluble cinnamon extract or placebo, return any pill bottles and will continue follow-up in the study. They will be encouraged to resume taking water-soluble cinnamon extract or placebo and blood work (if they choose) 6 months after delivery of their child. If the subject decides to re-start their water-soluble cinnamon extract or placebo, they will resume the study at their last documented visit (i.e. subject stops taking water-soluble cinnamon extract or placebo at Visit 4 and decides 1 year later that they wish to resume the study, their next visit would be Visit 6).

SUBJECTS ENROLLED NO LONGER PRE-DM: If a subject becomes no longer pre-diabetic while enrolled in the study, they will remain in the study.

SUBJECTS ENROLLED BECOME TYPE II DIABETIC: If a subject becomes Type II diabetic while enrolled in the study, they will be removed from the study.

SUBJECTS COMPLETING THE STUDY: When subjects have completed the study, the Pharmacy will de-identify the information and send to the Investigator for analysis. Each Associate Investigator will send the de-identified data to the Principal Investigator via an encrypted email for analysis.

HYPOGLYCEMIC EPISODES: If the subject experiences a hypoglycemic (low blood sugar) episode, e.g., for example heart palpitations (abnormal heart beats either fast or slow), tremors (involuntary muscle movement), hunger, sweating, they should be instructed to eat 15-20 grams of sugar (e.g., glucose (sugar) tablets, glass of juice or other snack containing sugar) then eat some carbohydrates (e.g., a small meal or cracker with peanut butter).

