BLOOD TEST OUTSIDE OF NORMAL REFERENCE RANGE: Research Coordinators at each site will print the blood test results and place in the subject's folder. If any of these results are outside of the normal reference range noted by their lab, they will place a telephone consult for the subject's Primary Care Manager (PCM).

DISPOSAL OF STUDY RELATED PILLS: Subjects will return any remaining study-related pills directly to the Research Coordinator or Principal Investigator. The Research Coordinator or Principal Investigator will be responsible for disposing of the study-related pills. The preferred method of disposal is to have the Pharmacy dispose of them. If the Pharmacy is unable to dispose of them, they will provide directions on safe disposal for the Research Coordinator or Principal Investigator to follow.

OTHER ITEMS: If at any time, a site needs more study medication, they should contact the main site at the Nellis AFB and request. Integrity Nutraceuticals should not be contacted directly. Prior to ordering any standard of care labs, study staff will verify in AHLTA that the subject did not have that lab test within the previous timeframes documented in the study visits above. In addition, CHCS has alerts built in that will alert the person entering the lab test that there is a pending order.

Subjects will take their water-soluble cinnamon extract or placebo daily and will be permitted to have the usual medical care for other co-morbid and acute conditions if applicable. Analysis described above using intention-to-treat principles for any missing data will be used (we will use the carry-forward method to impute missing data).

The placebo will be a gelatin capsule filled with wheat bran, which does not increase the risks to subjects.

Each site's Laboratory will be responsible for analyzing blood samples obtained at their site for this study. Samples will be labeled as they would for standard laboratory draws. All Laboratories follow Clinical Laboratory Improvement Amendments (CLIA) procedures when processing laboratory specimens mentioned in this research project.

This study involves the use of an investigational product (IP) called Cinnulin PF (water-soluble cinnamon extract). This means that the product has not been approved by the Food & Drug Administration (FDA) for preventing or delaying the onset of

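### The protocol fills any missing data by carry-forward, the SAP names a mixed model that needs no imputation, and the two are never reconciled; the H01 bias is small on average and larger in off-drug contrasts

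*Combined protocol and SAP*

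**What the plan says.** **The imputation rule.** Protocol Summary section 4 says that "the carry-forward method to impute missing data will be used" and presents this as part of intention-to-treat. Protocol section 3.6, Other Items, repeats it for any missing data: "we will use the carry-forward method to impute missing data". No outcome, visit or reason for missingness is exempted.

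**The model.** The SAP (protocol section 6.3) takes subject as random and treatment and time as fixed, and tests H01 by a mixed-effects repeated-measures ANOVA. If H01 is rejected, contrasts within clinically important time intervals follow. The SAP's power section describes these as one-tailed independent-sample t-tests. The SAP does not mention carry-forward. It states no missing-data assumption, no handling of incomplete series and no sensitivity analysis.

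**Sources of missing data.**
- Section 6.2 expects 428 of 557 to complete.
- Section 3.6, Withdrawal Procedures, says of subjects found to be diabetic that "they will be withdrawn and referred to their PCM to initiate standard of care treatment". A later paragraph agrees: "If a subject becomes Type II diabetic while enrolled in the study, they will be removed from the study". Planned conversion is 17.5% on placebo and 11.5% on extract.
- At Month 12, "SUBJECTS STOP TAKING STUDY MEDICATIONS AT THIS VISIT", while visits run on to "Visit 9-Month 24 (90 days after Visit 8").
- Stopping the drug does not by itself create missing data: "Regardless of the amount of missed doses, all subjects will remain in the study and continue with all the study related visits".

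**The concern.** For H01, carry-forward does three things in this design.

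1. A subject removed for diabetes on glucose or HbA1c is frozen at a value selected for crossing a threshold. Such values tend to be high for that subject, and more are expected on placebo. Lipids and waist are not the trigger, so this applies to them only weakly.
2. A subject last seen between Month 3 and Month 12 has an on-drug value copied into Months 15 to 24, when nobody is on drug.
3. Imputed values enter the analysis as if they had been measured.

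What is at stake is chiefly the reading of the second year. An effect that ended with dosing could look partly lasting, while an effect that grows over time could be understated.

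**Working it through.** **Expected loss.** 557 − 428 = 129, and 129/557 = 23.2%. This reproduces the plan's figure.

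**Share imputed at Month 24.** The plan does not say whether converters are among the 129, so both readings are shown.
- Converters on top of the 129: 1 − (1 − 0.232)(1 − 0.175) = 0.366 on placebo and 1 − (1 − 0.232)(1 − 0.115) = 0.320 on extract. By simulation it is 36% and 31%, slightly lower because a conversion found at Month 24 leaves no later visit to fill.
- Converters within the 129 (other dropout set at 11.0%): 1 − 0.89 × 0.825 = 0.266 and 1 − 0.89 × 0.885 = 0.212. By simulation it is 26% and 21%.

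**Bias in H01.** Inputs from the plan: correlation 0.8 and 8 repeated measures (SAP power run), the two conversion rates, and the loss figure. The H01 effect size f = 0.10 equals d = 0.20 SD with two equal groups. The power run has numerator df 1, so the visit-averaged group difference is the quantity closest to the planned test.

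Assumptions that are not in the plan: normal data with equal correlations; baseline below the threshold; equal dropout in both arms, with last visit uniform from baseline to Month 21; no drift. The target is the outcome had nobody been removed or lost.

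The conversion threshold is solved to give 17.5% on placebo. The constant and growing effects are then solved to give 11.5% on extract. The ended effect is fixed at 0.2 SD through Month 12 and zero afterwards.

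Each carry-forward cell gives converters on top of the 129 / converters within it. Figures are in SD, and positive favours extract.

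| True pattern | Quantity | True | Carry-forward |
|---|---|---|---|
| No effect | Visit average | 0 | 0.00 / 0.00 |
| Constant | Visit average | 0.197 | 0.209 / 0.212 |
| Growing to 0.396 | Visit average | 0.222 | 0.202 / 0.213 |
| Growing to 0.396 | Month 24 | 0.396 | 0.346 / 0.373 |
| 0.2, ends at Month 12 | Visit average | 0.099 | 0.129 / 0.125 |
| 0.2, ends at Month 12 | Months 15–24 | 0 | 0.053 / 0.043 |

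Repeat simulations give about 0.053 to 0.055 / 0.043 to 0.045 for the last row. The ended-effect row does not match the planned conversion: it implies about 14.9% on extract, not 11.5%. Imputed extract values at Month 24 are then about 34% / 23%.

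**Other cases.**
- Correlation 0.5: the ended effect shows 0.067 / 0.058 over Months 15–24.
- Lipids or waist (correlation 0.3 to 0.7 with the trigger): a constant effect moves by 0.00 to +0.01, and an ended effect shows about 0.03 to 0.05 over Months 15–24.
- No effect, dropout 18.2% v 28.2%, drift 0.4 SD: up to 0.013 on average and 0.027 at Month 24.
- Ended effect, loss about 13% v 33%, drift 0.5 SD: about 0.04 on average and 0.09 at Month 24.

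**The alternative.** A likelihood fit to the observed visits is within 0.003 SD of the target when loss depends on observed values. Independent t-tests on observed visits are not a substitute. They show about 0.13 at Month 24 for a constant 0.197, and about −0.04 over Months 15–24 for an ended effect, because removed converters drop out of the means.

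**The case against.** **The SAP does name an analysis.** A reader might infer that no method for H01 is named once carry-forward is dropped. The documents do not support that. The SAP names a mixed-effects model with a random subject effect, its power run uses one common correlation, and it lists SAS and R, which can fit such a model to incomplete series. What is missing is narrower: how the model is estimated, how incomplete series enter it, and which of the two rules governs.

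**The overall test is barely affected.** This stands. At the only alpha attached to H01 (0.000437), with 278 v 279 subjects, rejection under carry-forward v complete data is 21.6% v 25.1% for a constant effect and 3.5% v 2.0% for an ended effect.

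**The contrasts are gated.** This also stands. They run only if H01 is rejected, which in the ended-effect case happens in about 3.5% of trials at that alpha. The chance of a published false claim of a lasting effect is therefore smaller than the contrast bias alone suggests.

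**The target is assumed.** True. The plan says intention-to-treat but does not say what the outcome means for a removed converter. Another target would give other bias figures. That is a reason to state one.

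**Likelihood is not always better.** True. Suppose dropout depends on the unseen value, with odds ratios of 2 and 0.5 per SD in the two arms. With no effect, the likelihood fit is off by 0.025 to 0.03 and carry-forward by 0.02 to 0.03. With a true 0.194, likelihood gives 0.169 and carry-forward 0.186.

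**Conclusion.** The point holds as an unreconciled analysis rule with a modest effect. Carry-forward is prescribed for any missing data, the SAP's own model does not need it, and no target for converters or sensitivity analysis is given.

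Under the stated assumptions the visit-averaged bias is about 0.01 to 0.03 SD in either direction, and nil with no effect and equal dropout. In the off-drug contrasts it is about 0.04 to 0.055 SD if a 0.2 SD effect ends at Month 12. It is larger if correlation is lower, or if loss is unequal and values drift.

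A reader might infer that carry-forward always favours the extract or invalidates the H01 test. Neither follows. The sign depends on trajectories that the documents do not give, and the overall test moves little. A reader might also think that subjects who merely stop capsules are imputed, but the protocol keeps them in follow-up.

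The change should be made because it is cheap and the second year is the part most open to misreading. Confidence is medium, since the sizes rest on assumed trajectories, dropout pattern and target.

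**What to change.** 1. Remove carry-forward as the primary rule from Protocol Summary section 4 and from section 3.6, Other Items. Keep it at most as a sensitivity analysis.
2. In the SAP's Hypothesis Testing text, state that the mixed model for H01 is fitted for each outcome by REML to all observed visits, including the value that triggered removal. Include baseline, treatment, categorical visit and treatment-by-visit, with unstructured covariance, a named fallback if it does not converge, and no imputation.
3. Take the interval contrasts from this model, and amend the SAP's power section, which describes separate t-tests.
4. State the target for converters. This fit estimates the outcome had they not been removed; another target needs another method.
5. Add a missing-not-at-random sensitivity analysis, for example delta adjustment by arm.

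**Cost.** The change is wording, fixed before unblinding, plus a little more analysis in the software already listed. The triggering value must be noted from records for each removal. Unstructured covariance over 8 visits has 8 × 9/2 = 36 parameters, hence the fallback. At 278 v 279 the Month-24 standard error rises from about 0.056 to 0.060 SD (0.060/0.056 = 1.07), while the visit-averaged standard error falls from 0.042 to 0.038. The site counts in section 6.4 sum to 46 + 106 + 76 + 53 + 2 = 283; at 141 v 142 the Month-24 standard error would rise from 0.078 to 0.084.
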